# 7.2.8 Anticipated adverse events

Information regarding anticipated AEs for Sculptra is included in the study specific IFU.

## 7.2.9 Pregnancy

Pregnancy itself is not regarded as an AE.

If there is a pregnancy during the study period, the subject must be withdrawn from any following study treatment but should continue to be followed within the study and the outcome of pregnancy must be reported even if the delivery occurs after study completion.

A pregnancy confirmed during the study period must be reported by the Investigator on a pregnancy report form immediately upon acknowledge and be submitted to the CRO according to contact details specified in section 7.2.5.5. The report can be prospective or retrospective. Follow-up shall be conducted to obtain outcome information on all prospective reports.

Cases that led to fetal distress, fetal death or a congenital abnormality or birth defect are to be regarded as SAEs and shall be reported on the exposure *in utero* report form to the Sponsor immediately but no later than 24 hours after the Investigators awareness. These events shall be handled as SAEs during data processing. Other complications during the pregnancy that are related to the pregnant woman and fulfils any serious criteria, such as pre-eclampsia requiring hospitalization, shall be reported and handled as SAEs. Elective abortions without complications shall not be reported as AEs.

Print date:

2021-08-25 16:18

# 7.2.10 Device deficiencies

# 7.2.10.1 Definition of a device deficiency

A device deficiency is defined as an inadequacy of a medical device with respect to its identity, quality, durability, reliability, safety, or performance.

Note: Device deficiencies include malfunctions, use errors, and inadequate labelling.

## 7.2.10.2 Recording instructions for device deficiencies

In the event of a device deficiency, the Investigator shall send the completed clinical study complaint form to the CRO.

A device deficiency that led to a SAE and any device deficiency that could have led to a SAE shall be reported to the CRO within 72 hours after the Investigator's awareness (for contact information, see section 7.2.5.5). If the form is completed within an eCRF system, refer to the eCRF completion guidelines.

If the Investigator or the Sponsor assesses that the device deficiency could have led to a SAE the Sponsor is responsible for reporting the device deficiency to RA and the PI is responsible for reporting it to the REB.

The deficient study product shall be kept by the study center until the Sponsor has confirmed whether the product shall be returned to Sponsor for further study or if it can be destroyed at the study center.

#### 7.2.11 Stopping rule

Enrollment and injections at a study center will be temporarily halted if an SAE occurs for a vascular embolic event that leads to skin necrosis, vision loss, or stroke and is determined by the Investigator to be directly or possibly related to the investigational device or injection procedure.

The SAE will be investigated by the Sponsor. If the Sponsor's investigation concludes the SAE:

- was unanticipated
- directly related to the study product or device injection procedure and
- presents an unreasonable risk to study subjects,

the study will be terminated, and the Investigators notified. The REB and RA will also be notified if the study is prematurely terminated due to safety concerns.

If the SAE does not meet the above criteria, then enrollment in the study will continue provided all other safety criteria have been met.

#### STATISTICAL DESIGN AND ANALYSIS 8.

#### 8.1 General

All statistical analyses, including summary tables and data listings, will be performed using the SAS® system. Confidence intervals and p-values will be 2-sided and performed at a significance level of 5%.

<sup>2 Inadequacy of device safety refers to properties of the device which could have or have led to an AE.

2021-08-25 16:18

Continuous variables will be summarized using descriptive statistics, e.g. mean, median and standard deviation. Categorical variables will be presented in frequency tables with number and percent of observations for each level.

## 8.2 Analysis populations

The following populations will be defined:

• Safety Includes all subjects who were injected in at least one thigh

• Full Analysis Set (FAS) Includes all subjects who were injected in both thighs

FAS is the primary population for all effectiveness analyses.

If there are any clinical study protocol (CSP) deviations considered to have substantial impact on the effectiveness outcome, a per protocol (PP) population excluding those subjects may be defined.

Safety analysis is performed based on the safety population set.

The disposition of subjects will be presented in tables and/or figures as appropriate. The number of screened, treated, completed, and withdrawn subjects will be presented, as well as number of subjects in each analysis population set.

# 8.3 Demographics, baseline assessments, and subject characteristics

Demographic endpoints, baseline assessments, and subject characteristics will be presented based on the FAS, using descriptive statistics.

#### 8.4 Data Transformations

Responder rate (%) regarding GAIS will be calculated as (number of subjects (or thighs) being at least improved/number of subjects reporting at the specified visit)\*100.

Time to onset of an AE will be derived as the start date minus the date of most recent treatment. If the start date is missing, it will be assumed that the AE started on the day of most recent treatment.

Duration of an AE will be derived as the stop date minus the start date + 1. If the start date is missing, it will be assumed that the AE started on the day of most recent treatment. Missing stop date will not be imputed and therefore no duration will be calculated in these cases. Instead, the number of AEs that were ongoing at the end of the study will be given.

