### Safety objectives and endpoints

The safety objective is to evaluate the safety of Sculptra for the improvement in appearance of cellulite in the posterior thighs.

The safety endpoints are:

- 1. Incidence, intensity, time to onset and duration of adverse events (AEs) collected throughout the study period.
- Incidence, intensity, time to onset and number of days of pre-defined expected post-2. treatment events collected using subject diaries for 28 days from each treatment.

Doc id 43CASA2006 CSP Sculptra cellulite 🚣 GALDERMA MA-47276

Print date:

2021-08-25 16:18

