## 7.2.6 Follow-up of unresolved events ongoing at termination of the study

All serious as well as non-serious AEs with a causal relationship to the study product or treatment procedure and ongoing at study end, shall be followed up after the subject's participation in the study is over. Such events shall be followed-up after the last study visit until resolved, assessed as chronic or stable, or subject is lost to follow up. Follow-up information shall be reported on the AE follow-up form.

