#### 8.6 Safety analysis

AEs will be coded according to MedDRA and summarized by system organ class (SOC), preferred term (PT). The number of subjects with AEs related to study product or injection procedure as well as the number of events will be summarized by SOC, PT, and maximum intensity. In addition, for related AEs the number of days to onset and the duration of event will be summarized by SOC and PT using mean, SD, min, max and median. Action taken for related AEs will also be summarized. Serious AEs will be listed.

Non-related AEs will be summarized by SOC, PT, and maximum intensity.

Number and percentage of subjects reporting each pre-defined, expected, post-treatment symptoms, as collected in the 28 days diary, will be presented in total and by maximum severity for each treatment session.

2021-08-25 16:18

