5.6 Derived and Transformed Data

Variables requiring calculation will be derived using the following formulas:

 Responder rate (%) regarding GAIS will be calculated as (number of subjects (or thighs) being at least improved/number of subjects reporting at the specified visit)*100.

CCI

• Time to onset of an AE will be derived as the start date minus the date of most recent treatment. If the start date is missing, it will be assumed that the AE started on the day of most recent treatment.

• Duration of an AE will be derived as the stop date minus the start date + 1. If the start date is missing, it will be assumed that the AE started on the day of most recent treatment. Completely missing stop date will not be imputed and therefore no duration will be calculated in these cases. Instead, the number of AEs that were ongoing at the end of the study will be given.

Time to return to daily activities after treatment will be derived as the subject diary date/time with the first "Yes" for "Did you feel comfortable returning to daily activities today?" minus the date/time of the corresponding treatment session injection start time, and will be represented in days. Time to feeling comfortable returning to daily activities will be calculated for each diary (treatment session) separately.

Subjects who never report feeling comfortable during each session period will have their response date and time censored at the date and time of their last diary entry in each period.

- Time to onset of pre-defined expected post-treatment events collected using subject diaries will be derived as the first recorded event date minus the date of most recent treatment.
- Days A duration expressed in days between 1 date (date1) and another later date (date2) will be calculated using the following formula: duration in days = date2 – date1 + 1
- Months A duration expressed in months is calculated as the number of days divided by 365.25/12 (approximately 30.4)
- Years A duration expressed in years is calculated as the number of days divided by 365.25
- Change from baseline Change from baseline will be calculated as: Change = post baseline value – baseline value

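### Duration of related AEs is summarised over resolved events only; unresolved events appear only as a count not tied to SOC/PT, so the summary is biased short whenever a related AE is unresolved

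*Protocol*

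**What the plan says.** Safety endpoint 1 in the protocol is "Incidence, intensity, time to onset and duration of adverse events (AEs) collected throughout the study period". The derivation in Protocol 8.4 is "Duration of an AE will be derived as the stop date minus the start date + 1". When the stop date is absent, "Missing stop date will not be imputed and therefore no duration will be calculated in these cases". The next sentence gives the replacement: "Instead, the number of AEs that were ongoing at the end of the study will be given". SAP 5.6 carries both parts over, with one added word: "Completely missing stop date will not be imputed and therefore no duration will be calculated in these cases".

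Protocol 8.6 then says that, for related AEs, "the duration of event will be summarized by SOC and PT using mean, SD, min, max and median". SAP 8.1 keeps the summary by SOC and PT. Its list of AE outputs does not mention the number ongoing.

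Three other provisions bear on the point.

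- **Protocol 7.2.6**, on related AEs still present at study end: "Such events shall be followed-up after the last study visit until resolved", or until judged chronic or stable, or the subject is lost. Neither document says whether stop dates obtained this way enter the duration table.
- **SAP 5.6**, on return to daily activities: a subject who never reports it is "censored at the date and time of their last diary entry in each period". The SAP thus already censors one time-to-event measure.
- **SAP 5.9.1** sets a completely missing AE stop date to the discontinuation or end-of-study date, unless the outcome is ongoing or unknown.

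**The concern.** An event is left out of the duration statistics when it has not ended by last contact, and the longer an event lasts the likelier that is. The statistics are then conditional on resolution and, on average, too short.

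The short-lived reactions (pain, tenderness, redness, bruising, swelling, itching) are asked about in the diary, and Protocol 7.2.1 displays diary data apart from other AE data. The AE duration table will therefore lean towards events such as papules, nodules and induration. Protocol 2.3 lists these among the most common reactions and says that most, not all, resolve with time. Protocol 2.1 says the sponsor will use this pilot to start a pivotal study if results are favourable. A short median for nodules, computed from resolved nodules alone, could be misread in that decision.

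**Working it through.** The plan states no AE duration and no expected share of unresolved events, so there is no figure to reproduce. The check has three parts.

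**1. Illustrative size**

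Inputs from the documents: one month is 4 weeks, so Month 12 is 12 × 28 = day 336.

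Assumptions: onset on day 60, shortly after a nominal third session at week 8 (day 56); durations exponential with true median M; no stop date after the last visit is used.

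Observed time C = 336 − 60 = 276 days. Rate r = ln 2 / M. Share resolved F = 1 − exp(−rC). Median among resolved events = −ln(1 − F/2) / r.

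| True median M (days) | Unresolved, 1 − F | Reported median (days) | Shortfall |
|---|---|---|---|
| 7 | 0% | 7.0 | 0% |
| 21 | 0.01% | 21.0 | 0% |
| 90 | 12% | 75.4 | 16% |
| 180 | 35% | 102.9 | 43% |
| 365 | 59% | 120.1 | 67% |

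For M = 180: r = 0.6931/180 = 0.00385; F = 1 − exp(−1.063) = 0.6545; reported median = −ln(1 − 0.3273)/0.00385 = 102.9.

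As M grows, resolved durations become uniform on 0 to 276 days, so under this model the reported median approaches 276/2 = 138 days.

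*Sensitivity to observed time.* The visit windows put follow-up after a third session between 336 − 14 − 84 = 238 and 336 + 14 − 56 = 294 days. For M = 90, 180 and 365 the reported medians are 70.7, 92.6 and 105.7 at 238 days, and 77.2, 107.4 and 126.7 at 294 days.

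**2. A count without a distribution**

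Suppose 20 related AEs, 17 resolved with a mean of 10 days and 3 unresolved after 280 days (336 − 56). These counts are invented for the example. The planned mean is 10 days. Entering the three at the time already observed gives (17 × 10 + 3 × 280)/20 = 50.5 days, which is itself a lower bound. With no unresolved event both figures are 10.

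**3. The two SAP rules side by side**

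| Provision | Completely missing stop date |
|---|---|
| SAP 5.6 | Not imputed; no duration |
| SAP 5.9.1 | Set to discontinuation or end of study, unless outcome is ongoing or unknown |

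Protocol 7.2.5.3 also has outcome codes for chronic or stable events and for events not recovered at study end. Neither is in the SAP 5.9.1 exemption. Read literally, a nodule with either code gets an end-of-study stop date under 5.9.1 and no duration under 5.6.

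SAP 5.9 names only treatment-emergent status, and prior or concomitant status of therapies, as uses of imputed dates. SAP 8.1 defines treatment-emergent from the start of the event, so an imputed AE stop date has no stated use. If it did reach the duration formula, an unresolved event would be treated as having ended on its last day. That understates the mean too, though by less than leaving the event out.

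**The case against.** A reader might infer that the longest reactions vanish from the report, or that the reported duration is bound to be too short. The documents do not support either reading.

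- The number of ongoing AEs is promised in both documents. A short median with most nodules unresolved would come with a large ongoing count.
- SAP 5.1 plans by-subject listings of eCRF data, and SAP 5.9 refers to AE listings with actual dates. With about 30 subjects, each unresolved event should be traceable.
- There is no bias if every related AE resolves with a recorded date. Some missing stop dates may belong to events that ended on an unknown day, so not every excluded event is long.
- Follow-up under Protocol 7.2.6 may supply later stop dates, and the duration formula does not exclude them. The 138-day ceiling holds only if they are not used.
- The scenarios of 90 days or more are assumptions. Protocol 6.3.3 says common injection reactions typically settle within a week, although its list does not include nodules.
- Kaplan-Meier estimates by PT in a pilot of this size would be sparse, and several events in one subject are not independent.
- The table shells are a separate document and may already show numbers ongoing per PT.

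All of this stands as a limit on the point, and it rules out a claim of concealment or of a known bias. It does not remove the mechanism. A single count does not correct a median or say which PT it belongs to. Time elapsed for unresolved events is not summarised. Events that end follow-up as chronic or stable never acquire a stop date on resolution. An event unresolved at early withdrawal may not be counted as ongoing at study end.

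**Conclusion.** The point holds in conditional form. The planned statistics for related AEs describe resolved events only, and they are biased short on average if any related AE is unresolved at last contact. If none is, they are unbiased.

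The size cannot be obtained from the documents. Under the exponential illustration it is nil for reactions of days to weeks, and the reported median falls short by about 16%, 43% and 67% at true medians of 90, 180 and 365 days. Those percentages rest on the assumed distribution, 276 days of observation and no use of post-study stop dates.

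The mismatch between SAP 5.6, SAP 5.9.1 and the protocol's outcome codes is a separate defect of wording. It need not alter the duration table, because SAP 5.9 does not name duration as a use of imputed dates, but the intended handling is left open. This is a change worth making before database lock. It does not affect the primary endpoint.

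**What to change.** In Protocol 8.6 and SAP 8.1:

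1. Keep the present descriptive statistics and label them as resolved events only.
2. Beside them, per SOC and PT, give the number of related AEs resolved, the number unresolved, and for the unresolved the time observed to last contact. Count events unresolved at early withdrawal as unresolved.
3. Add a Kaplan-Meier summary from start date to stop date, with unresolved events censored at last contact. Do this for related AEs overall, and for each PT that has an unresolved event and enough events to support it.
4. State that stop dates from the Protocol 7.2.6 AE follow-up form are used if available at database lock.
5. In SAP 5.6 and 5.9.1, state that end-of-study dates imputed for completely missing stop dates are not used for duration, and align the exemption with the outcome codes in Protocol 7.2.5.3.

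The cost is SAP and protocol wording, two count columns and one further table. SAS/STAT is already listed in SAP section 10, and no new data are collected. The drawbacks are few events per PT, several events per subject (so the estimates are descriptive and naive standard errors should not be relied on), and medians that may not be reached. If nothing is unresolved, the added summary does no harm.

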# 8.5 Efficacy analysis

#### 8.5.1 Primary analysis

The GAIS assessment by the Treating Investigator at Month 9 will be presented in a frequency table. In addition, the proportion of improved subjects (assessed as at least improved on both thighs) will be presented together with a 95% confidence interval (based on the binomial distribution).

If the PP population contains less than 90% of the FAS population the primary analysis will be repeated using the PP population.

Print date:

2021-08-25 16:18

#### 8.5.2 Secondary analysis

The GAIS assessment by the Treating Investigator will be presented in frequency tables. In addition, the proportion of improved thighs (assessed as at least improved) will be presented together with a 95% confidence interval (based on the binomial distribution). This will be done for each thigh separately and also for both thighs combined at Month 1, 2, 6, 9 and 12.

The GAIS assessment by the subject will be presented in frequency tables. In addition, the proportion of improved thighs (assessed as at least improved) will be presented together with a 95% confidence interval (based on the binomial distribution). This will be done for each thigh separately and also for both thighs combined at Month 1, 2, 6, 9 and 12.

#### 8.6 Safety analysis

AEs will be coded according to MedDRA and summarized by system organ class (SOC), preferred term (PT). The number of subjects with AEs related to study product or injection procedure as well as the number of events will be summarized by SOC, PT, and maximum intensity. In addition, for related AEs the number of days to onset and the duration of event will be summarized by SOC and PT using mean, SD, min, max and median. Action taken for related AEs will also be summarized. Serious AEs will be listed.

Non-related AEs will be summarized by SOC, PT, and maximum intensity.

Number and percentage of subjects reporting each pre-defined, expected, post-treatment symptoms, as collected in the 28 days diary, will be presented in total and by maximum severity for each treatment session.

2021-08-25 16:18

# 8.7 Handling of missing data

Study data will be presented on observed cases, i.e.no imputation of missing values will be performed. Exception: when calculating duration and time to onset for AEs where start date is missing. If the start date is missing, it will be assumed that the AE started on the day of most recent treatment.

# 8.8 Interim analysis

No applicable as this is an open study.

## 8.9 Data monitoring committee

Not applicable.

#### 8.10 Withdrawals and deviations

All withdrawn subjects will be listed individually, including at least subject number, date and reason for withdrawal, and last visit performed.

Subjects with CSP deviations will be listed individually, including subject number and observed deviation. Depending on the seriousness of the deviation, subject might be excluded from the PP population, which shall be documented prior to database lock.

Deviations from the statistical plan will be documented in the clinical report.

# 8.11 Sample size

The sample size of approximately 30 subjects is not based on a statistical calculation. The selected number of subjects is regarded as enough for an evaluation of safety and effectiveness in this pilot study.

#### 9. DATA MANAGEMENT

Data management based on GCP refers to the activities defined to achieve safe routines to enter clinical data information into a database, efficiently and avoiding errors. The data management routine includes procedures for database set-up and management, data entry and verification, data validation, and documentation of the performed activities including information of discrepancies in the process. The data management process will be described in detail in the data management plan (DMP).

The database, the data entry screens and program will be designed in accordance with the CSP and the CRF template. Data validation will be performed by computerized logical checks and manual review. Drugs and events will be coded in accordance with World Health Organization (WHO) Drug and medical dictionary for regulatory activities (MedDRA) dictionaries as specified in the DMP. Safety data (SAE and if applicable AE of special interest) in the clinical database will be reconciled against the data in the safety database.

When all efforts have been made to ensure that the data recorded in the eCRFs and entered in the database is as correct and complete as possible, the clinical database will be locked. Study data will be transferred to SAS datasets, which thereafter will be write-protected. Statistical analyses will be generated in SAS using data from the locked datasets.

